Appendix 2: Clinical Laboratory Evaluations

Clinical Chemistry Panel (Fasted):	Hematology Panel:	Other Tests:						
(Fasted):	Hematocrit Hemoglobin Mean corpuscular hemoglobin Mean corpuscular hemoglobin concentration Mean corpuscular volume Platelet count Red blood cell (RBC) count RBC distribution width White blood cell (WBC) count WBC differential (percent and absolute): Basophils Eosinophils Lymphocytes Monocytes Neutrophils	Hemoglobin A1c (HbA1c) ^b Thyroid-stimulating hormone (TSH) ^b Estimated glomerular filtration rate ^{a,d} SARS-CoV-2 (COVID-19) test Coagulation Parameters: Partial thromboplastin time Prothrombin time International normalized ratio Serology: ^b Hepatitis B surface antigen (HBsAg) Hepatitis B virus (HBV) immunoglobulin M (IgM) core antibody Hepatitis C virus (HCV) antibody Human immunodeficiency virus (HIV) antibody						
	Secretaria (Sec. Sec.)	For Female Subjects Only: Pregnancy test (serum qualitative, serum quantitative may be used for confirmation if needed) ^c Follicle-stimulating hormone						
Luina Dana Canara 2	Urinalysis: Bilirubin Color and appearance Glucose							
Urine Drug Screen: ^a Including but not limited to the following: Alcohol (ethanol) ^e Amphetamines Barbiturates Benzodiazepines Cannabinoids Cocaine (metabolite) Methadone Opiates Phencyclidine Cotinine	Ketones Leukocyte esterase Nitrite Occult blood pH and specific gravity Protein Urobilinogen Microscopic examination including bacteria, casts, crystals, epithelial cells, RBCs, and WBCs (if protein, leukocyte esterase, nitrite, or occult blood is positive)	(post-menopausal female subjects only) ^b						

- a. Performed at Screening and Check-in (Day -1) only.
- b. Performed at Screening only.
- c. Performed at Screening, Check-in (Day -1), and Day 14 for End of Treatment (EOT) or Early Termination (ET) only.
- d. Calculated using the Chronic Kidney Disease Epidemiology Collaboration (CKD-EPI) equation.
- e. Urine or breath test.

Appendix 3: Total Blood Volume

The following blood volumes will be withdrawn for each subject:

Assessment	Approximate Blood Volume per Sample (mL)		Approximate Total Volume (mL) 8.0 4.0 156.0		
Serology	8.0	1			
Hemoglobin A1c (HbA1c)	4.0	1			
LOXO-305 Pharmacokinetic (PK) sampling	4.0	39			
Clinical laboratory evaluations:					
Hematology	4.0		((0		
Clinical chemistry ^a	4.0	6	66.0		
Coagulation	3.0				
Serum pregnancy test (female subjects only)	4.0	3	12.0		
Serum follicle-stimulating hormone (post-menopausal female subjects only)	4.0	1	4.0		
	- 9	Total:	250.0 mL		

^a Thyroid stimulating hormone (TSH) and estimated glomerular filtration rate (eGFR) will be assessed as part of the clinical chemistry sample.

If extra blood samples are required, the maximum blood volume to be withdrawn per subject will not exceed 500 mL.

Appendix 4: Schedule of Assessments

CONFIDENTIAL Protocol Reference: LOXO-BTK-20009 Covance Study: 8419688

	Screening (Days -29 to -2)	Check-in (Day -1)	Period 1									Pe	eriod	12	Clinic Discharge/ EOT/ET ^t	Follow-up Phone Call (EOS)		
Study Procedures ^a			1	2	3	4	5	6	7	8	9	10	11	12	13	14	15	7 (± 2) days post EOT/ET ^u
Confined to the CRU		X	X	X	X	X	X	X	X	X	X	X	X	X	X	X	X	
Inclusion/Exclusion Criteria	X	X																
Informed Consent	X																	
Demographics	X						la i											
Medical History	X	X^{b}				3 9	ki 4											
Height/Weight/BMI	Xc	X			ž. –		8) (4			8						8 1	Ÿ.	
Physical Examination ^d	73 (5	X		8			5,0 5,										X	
12-lead ECGe	X	X	X			X	60. 0			X		,	X			W-	X	
Vital Sign Measurements ^{f,g,h}	X	X	X	X	X	X	X	X	X	X	X	X	X	X	X	X	X	
HDYF? Inquiryi	X	X	X	X	X	X	X	X	X	X	X	X	X	X	X	X	X	X
AEs/SAEs ^j	X	X	X	X	X	X	X	X	X	X	X	X	X	X	X	X	X	X
LOXO-305 Dosing			Xk				20 20			X^1						8		
CCI																		
Clinical Laboratory Evaluations ⁿ	X	X				X			X				X			X	X	
eGFR	X	X																
Hepatitis and HIV Screen	X																	
COVID-19 Screen ^o	X	X																
HbA1c Test	X						J.	J		ý								
Drug Screen ^p	X	X				s												
Prior and Concomitant Medications ^q	X	X	X	X	X	X	X	X	X	X	X	X	X	X	X	X	X	X
Serum Pregnancy Test ^r	X	X		30 al	(-)II											X	X	
FSH Test ^s	X			-														
TSH Test	X																	

Abbreviations: AE = adverse event; BMI = body mass index; BP = blood pressure; COVID-19 = SARS-CoV-2; CRF = Case Report Form; CRU = Clinical Research Unit; ECG = electrocardiogram; eGFR = estimated glomerular filtration rate; EOS = End of Study; EOT = End of Treatment; ET = Early Termination; FSH = follicle-stimulating hormone; HbA1c = hemoglobin A1c; HDYF? = How Do You Feel?; HIV = human immunodeficiency virus; ICF = Informed Consent Form; PK = pharmacokinetic; SAE = serious adverse event; TSH = thyroid-stimulating hormone; UA = urinalysis.

a. For details on study procedures, see Section 7.

- b. Interim medical history only.
- c. Height collected at Screening only; BMI calculated based on Screening height.
- d. A complete physical examination will be performed at Check-in (Day -1). An abbreviated physical examination will be performed at Day 15 (EOT) or at ET.
- e. 12-lead ECGs will be obtained at Screening and Check-in (Day -1), Day 1 (predose), Day 4 (72 hours postdose on Day 1), Day 8 (predose), Day 11 (72 hours postdose on Day 8), and Day 15 (168 hours postdose on Day 8 [EOT]) or ET. 12-lead ECGs will be collected after the subject has rested in the supjne position for at least 10 minutes. When scheduled at the same time as PK blood draws, 12-lead ECGs will be obtained prior to and as close as possible to having blood drawn. The allowed sampling window for 12-lead ECGs is ± 30 minutes from the nominal timepoint for all postdose 12-lead ECGs and no less than 10 minutes prior to dosing for predose 12-lead ECGs.
- f. Vital sign measurements (supine BP and pulse rate) will be obtained at Screening, Check-in (Day -1), Day 1 (predose, 2 hours after dosing), daily on Days 2 through 7 (24, 48, 72, 96, 120, and 144 hours postdose on Day 1), Day 8 (predose, 2 hours after dosing), daily on Days 9 through 14 (24, 48, 72, 96, 120 and 144 hours postdose on Day 8), and on Day 15 (168 hours postdose on Day 8 [EOT]) or ET. Blood pressure and pulse rate will be measured using the same arm for each reading after the subject has been supine for at least 5 minutes. When scheduled at the same time as PK blood draws, vital sign measurements should be carried out prior to and as close as possible to having blood drawn. The allowed sampling window for vital sign measurements is ± 30 minutes from the nominal timepoint for all postdose vital sign measurements and no less than 10 minutes prior to dosing for predose vital sign measurements.
- g. Respiratory rate and body temperature will be obtained at Screening, Check-in (Day -1), and Day 15 (168 hours postdose on Day 8 [EOT]) or ET.
- h. Oxygen saturation will be measured via pulse oximetry at Screening, Check-in (Day -1), predose on Day 1, and Day 15 (EOT; 168 hours postdose on Day 8) or ET. The allowed sampling window for oxygen saturation measurements is ± 30 minutes from the nominal timepoint for all postdose oxygen saturation measurements and no less than 10 minutes prior to dosing for predose oxygen saturation measurements.
- i. A HDYF? inquiry will be performed at Screening (after the ICF is signed), at Check-in (Day 1), at each postdose vital sign measurement, and at an appropriate time for all other days.
- i. Adverse events and SAEs will be collected beginning at informed consent. Adverse events will be recorded throughout the study (ie, from signing of the ICF until EOS, or until ET if the subject discontinues from the study and does not complete a follow-up phone call), either as subject medical history (if the event is reported as beginning prior to signing of the ICF or if the event occurs prior to study drug administration on Day 1 and is assessed as not related to study procedures by the Investigator [or designee]) or as AEs (if the event occurs after signing of the ICF but prior to study drug administration on Day 1 and is assessed by the Investigator [or designee]) as related to study procedures, or if the event occurs after study drug administration on Day 1 through EOT or ET regardless of relationship to study drug). From EOT or ET through EOS, only AEs assessed as related to study drug are to be recorded. All SAEs that develop from the time of ICF signing until EOS (or ET if the subject discontinues from the study and does not complete a follow-up phone call) are to be reported.
- k. On Day 1, LOXO-305 will be administered in the morning, either following a fast of at least 10 hours prior to and 4 hours after LOXO-305 administration (with water restricted for 1 hours prior to and 4 hours after LOXO-305 administration (with water restricted for 1 hours prior to and 4 hours after LOXO-305 administration (with water restricted for 1 hours prior to and 4 hours after LOXO-305 administration (with water restricted for 1 hours prior to and 4 hours after LOXO-305 administration (with water restricted for 1 hours prior to and 4 hours after LOXO-305 administration (with water restricted for 1 hours prior to and 4 hours after LOXO-305 administration (with water restricted for 1 hours prior to and 4 hours after LOXO-305 administration (with water restricted for 1 hours prior to and 4 hours after LOXO-305 administration (with water restricted for 1 hours prior to and 4 hours after LOXO-305 administration (with water restricted for 1 hours prior to and 4 hours after LOXO-305 administration (with water restricted for 1 hours prior to and 4 hours after LOXO-305 administration (with water restricted for 1 hours prior to and 4 hours after LOXO-305 administration (with water restricted for 1 hours prior to and 4 hours after LOXO-305 administration (with water restricted for 1 hours prior to and 4 hours after LOXO-305 administration (with water restricted for 1 hours prior to a hours after LOXO-305 administration (with water restricted for 1 hours prior to a hours after LOXO-305 administration (with water restricted for 1 hours prior to a hours after LOXO-305 administration (with water restricted for 1 hours prior to a hours after LOXO-305 administration (with water restricted for 1 hours prior to a hours prior to a hours after LOXO-305 administration (with water restricted for 1 hours prior to a hours prior to a hours after LOXO-305 administration (with water restricted for 1 hours prior to a hours prior to a hours after the lox prior to a hours after the lox prior to a hours after the lox prior to a hours prior to and 1 hour post-LOXO-305 administration) or approximately 30 minutes after the start of a high-fat breakfast (with water restricted for 1 hour prior to and 1 hour post-LOXO-305 administration), according to the treatment sequence the subject is randomly assigned to. High-fat breakfast should be entirely consumed within 30 minutes.
- 1. On Day 8, LOXO-305 will be administered in the morning at approximately the same time as LOXO-305 was administered on Day 1 (+/- 15 minutes), either following a fast of at least 10 hours prior to and 4 hours after LOXO-305 administration (with water restricted for 1 hour prior to and 1 hour post-LOXO-305 administration) or approximately 30 minutes after the start of a high-fat breakfast (with water restricted for 1 hour prior to and 1 hour post-LOXO-305 administration), according to the treatment sequence the subject is randomly assigned to. High-fat breakfast should be entirely consumed within 30 minutes.

- n. Clinical chemistry panel (fasted for at least 8 hours), coagulation parameters, hematology panel, and UA will be performed at Screening, Check-in (Day -1), Day 4 (72 hours postdose on Day 1), Day 7 (144 hours postdose on Day 1), Day 11 (72 hours postdose on Day 8), and Day 14 (144 hours postdose on Day 8, if the subject completes the study [EOT]), or on the day of ET. At ET or the day before EOT (Day 14), subjects are not required to be fasted prior to clinical laboratory evaluations.
- o. Testing for COVID-19 will be conducted at a minimum at Screening and Check-in (Day -1). Testing for COVID-19 may also be conducted periodically during the subject's CRU confinement, at the discretion of the Investigator (or designee). Tests will be performed by rapid polymerase chain reaction or equivalent.
- p. Urine drug screen for drugs of abuse (including cotinine) and alcohol screen (urine or breath).

CONFIDENTIAL Protocol Reference: LOXO-BTK-20009 Covance Study: 8419688

- q. Prior and concomitant medication administration will be recorded beginning at informed consent. In addition, all Investigator-approved prescription and over-the-counter medications taken by a subject within 14 days or 5 half-lives (if known), whichever is longer, prior to Day 1 will be recorded on the subject's electronic CRF.
- r. Female subjects only. Performed at Screening, Check-in (Day -1), and Day 14 (144 hours postdose on Day 8), if the subject completes the study (EOT) or on the day of ET.
- s. Post-menopausal female subjects only.
- t. End of Treatment is defined as when the subject is released from the CRU following completion of all assessments through Day 15. Early Termination is defined as when the subject is released from the CRU if the subject terminates the study early. Vital sign measurements, ECG, and abbreviated physical examination results are to be available for review by the Investigator (or designee) prior to subject release from the CRU on Day 15 (EOT) or ET, Clinical laboratory results (for clinical chemistry, hematology, coagulation, and UA) and serum pregnancy test results (female subjects only) are to be available for review by the Investigator (or designee) prior to subject release from the CRU at the EOT visit and prior to subject release from the CRU at the ET visit, if available.
- u. To be conducted 7 days (± 2 days) following EOT or ET. End of Study is defined as when the subject is contacted by the CRU for a follow-up phone call 7 days (± 2 days) after the EOT visit or ET visit to determine if any SAE or study drug-related AE has occurred since the EOT or ET visit. All subjects who received LOXO-305 (including subjects who are terminated early) will receive a follow-up phone call.

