4.2. Check-in Procedures (Day -1)

At Check-in (Day -1), subjects will report to the CRU and the following procedures will be performed:

- 1. Review of inclusion/exclusion criteria
- 2. Interim medical history, including concomitant medication(s)
- 3. Weight and BMI

- 4. Complete physical examination (Section 7.2.5)
- 5. 12-lead ECG measured after the subject has been resting in the supine position for at least 10 minutes (Section 7.2.4)
- 6. Vital sign measurements (including body temperature, respiratory rate, oxygen saturation, and supine BP and pulse rate [measured after the subject has been supine for at least 5 minutes]; Section 7.2.3)
- 7. HDYF? inquiry, AE, SAE, and concomitant medication evaluations (Section 7.2.1)
- 8. Clinical laboratory evaluations (Section 7.2.2; clinical chemistry panel [fasted at least 8 hours], coagulation parameters, hematology panel, and UA; Appendix 2)
- 9. Screen for COVID-19 via PCR test (or equivalent; Appendix 2)
- 10. Urine drug screen for selected drugs of abuse (including cotinine) and alcohol screen (breath or urine; Appendix 2)
- 11. eGFR calculated using the CKD-EPI equation (Appendix 2)
- 12. Serum pregnancy test (for female subjects only; Appendix 2)
- 13. Compliance with concomitant medications and exclusionary restrictions (Section 6)

For subjects to continue their participation in the study, the inclusion/exclusion criteria must continue to be met at Check-in (Day -1 [as appropriate; #1, Section 4.2]). In addition, continued compliance with concomitant medication and other restrictions will be verified.

The Sponsor will review medical history and all screening evaluations for potential subjects prior to Check-in (Day -1). Prior to dosing, the Sponsor will provide approval of subjects selected for enrollment by the Investigator (or designee).

Subjects who meet all the inclusion criteria and for whom none of the exclusion criteria apply will be eligible to be enrolled into the study. Safety evaluations may be repeated at the discretion of the Investigator (or designee) or Sponsor.

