6.2. Diet, Fluid, and Activity Control

Subjects are required to refrain from use of tobacco, smoking-cessation products, and nicotine-containing products and e-cigarettes (nicotine and non-nicotine), within 3 months prior to Screening through EOT or ET.

Consumption of foods or beverages containing grapefruit/grapefruit juice or Seville oranges or its juice within 7 days prior to Check-in (Day -1) and through EOT or ET will not be allowed.

Consumption of alcohol- or caffeine-containing foods or beverages within 72 hours prior to Check-in (Day -1) and through EOT or ET will not be allowed.

Subjects will refrain from strenuous exercise from 5 days prior to Check-in (Day -1) and during the period of confinement at the CRU and will otherwise maintain their normal level of physical activity through EOT or ET (ie, should not begin a new exercise program or participate in any unusually strenuous physical exertion).

In Treatment A, subjects will be fasted for at least 10 hours prior to dosing until 4 hours postdose, after which a meal will be provided. Water will be restricted for 1 hour prior to and 1 hour after dosing. In Treatment B, subjects will consume a high-fat breakfast (contents are detailed in Table 3) before dosing. Aside from the 240 mL of water to be ingested with Treatment A and Treatment B, water will be restricted for 1 hour prior to and 1 hour after

dosing. The high-fat breakfast should contain between 800 to 1000 calories (comprising approximately 150 calories from protein, 250 calories from carbohydrates, and 500 – 600 calories from fat). Subjects should start the meal 30 minutes prior to administration of LOXO-305 and eat this meal in 30 minutes or less. LOXO-305 should be administered 30 minutes after start of the meal.

Administration of LOXO-305 in Treatments A and B (on Day 1 or Day 8) should occur at approximately the same time (ie, within 5 minutes).

Table 3: High-fat Breakfast Content

High-fat Breakfast

- 2 eggs fried in butter
- 2 strips of bacon
- 2 slices of toast with butter
- 4 oz of hash brown potatoes (fried with butter)
- 8 oz (240 mL) of whole milk

While confined at the CRU, subjects will receive a standard diet at scheduled times that do not conflict with other study-related activities.

Fasting requirement in relation to dosing are described in Section 3.1 and Section 5.2.

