7.2.2. Clinical Laboratory Evaluations

Clinical laboratory evaluations (clinical chemistry panel [fasted at least 8 hours; at ET or the day before EOT, subjects are not required to be fasted prior to clinical laboratory evaluations], coagulation parameters, hematology panel, TSH [Screening only], HbA1c [Screening only], eGFR [Screening and Check-in (Day -1)], and UA) will be collected at the timepoints specified in Appendix 4.

Screens for HCV antibody, HBsAg, HBV IgM core antibody, and HIV antibody will be performed at Screening.

Testing for COVID-19 via PCR (or equivalent) will be performed at the timepoints specified in Appendix 4. Testing for COVID-19 may also be conducted periodically during the subject's CRU confinement, at the discretion of the Investigator (or designee). Further details regarding COVID-19 testing (including procedures for subjects who test positive at any time throughout CRU confinement) are specified in a separate document.

A urine drug screen for selected drugs of abuse (including cotinine) and an alcohol screen (urine or breath) will be performed at Screening and repeated at Check-in (Day -1) for all subjects. A serum qualitative pregnancy test (female subjects only [serum quantitative may be used for confirmation, if needed]) and an FSH test (post-menopausal female subjects only) will be performed at the timepoints specified in Appendix 4.

The number of blood samples and total blood volume required for clinical laboratory evaluations are presented in Appendix 3. A list of the specific evaluations is in Appendix 2.

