## 1. INTRODUCTION

This SAP has been developed after review of the clinical study protocol (Final Version 1.0 dated 1 December 2020) and electronic case report form.

This SAP describes the planned analysis of the pharmacokinetic (PK) and safety and tolerability data from this study. A detailed description of the planned TFLs to be presented in the clinical study report (CSR) is provided in the accompanying TFL shells document.

In general, the analyses are based on information from the protocol, unless they have been modified by agreement with Loxo Oncology, Inc. A limited amount of information about this study (eg, objectives, study design) is given to help the reader's interpretation. This SAP must be finalized prior to the lock of the clinical database for this study. When the SAP and TFL shells are approved, they will serve as the template for this study's CSR.

This SAP supersedes any statistical considerations identified in the protocol; where considerations are substantially different, they will be so identified. If additional analyses are required to supplement the planned analyses described in this SAP, they may be performed and will be identified accordingly in the CSR. Any substantial deviations from this SAP will be agreed with Loxo Oncology, Inc. and identified in the CSR.

This SAP is written with consideration of the recommendations outlined in the International Conference on Harmonisation (ICH) E9 guideline *Statistical Principles for Clinical Trials* and ICH E3 guideline *Structure and Content of Clinical Study Reports*.

The document history is presented in [Appendix 1](#).

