#### 8.1.1. Calculation of the Summary Statistics

For continuous data the following rules will be applied:

- Missing values will not be imputed, unless specifically stated otherwise.
- Unrounded data will be used in the calculation of summary statistics.
- If the number of subjects with valid observations (n) <3, summary statistics will not be calculated, with the exception of n, minimum, and maximum.
- As ET data is not associated with any scheduled timepoint, it will be excluded from all calculations of summary statistics.
- Postdose repeats and unscheduled assessments will not be included in calculation of summary statistics.

For categorical data the following rules will be applied:

- If the categories of a parameter are ordered (eg, AE severity), all categories between the possible minimum and maximum categories will be included, even if n = 0 for a given category. If the categories are not ordered (eg, race), only those categories for which there is at least 1 subject represented will be included.

- Missing values will not be imputed, with the exception of AEs where the ‘worst-case’ approach will be taken (see [Section 8.6.1](#)), or unless specifically stated otherwise. A ‘missing’ category will be included for any parameter for which information is missing. This will ensure that the population size totals are consistent across different parameters.

All protocol deviations and data issues (eg missing data, out of protocol window) that occur during the study, including those related to COVID-19, will be considered prior to database lock for their severity/impact on how the data will be displayed.

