**Table 4: Clinical laboratory parameters Study day**

Period	Period Specific Study Day						
	Baseline	Day 2	Day 3	Day 4	Day 5	Day 6	Day 7
1	Day -1			4			7*
2	Day 7 Period 1			10			14

\*Day 7 measurements will be summarized at day 7 for period 1 used as baselines for the period 2.

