#### **8.6.2. Clinical Laboratory Parameters**

All clinical laboratory parameters, with changes from baseline will be listed; any value outside the clinical reference range will be flagged, and whether the out of range value was deemed clinically significant or not clinically significant will be indicated. Separate listings will be provided for any parameter for which there is any individual subject value outside the respective clinical reference range.

The observed results and change from baseline for clinical chemistry, hematology, and coagulation parameters will be summarized descriptively by treatment and period specific timepoint.

Values recorded as  $< x$ ,  $\leq x$ ,  $> x$ , or  $\geq x$  will be displayed in the listings as recorded. For the derivation of listing flags, calculation of summary statistics, and presentation in the figures,  $< x$  and  $\leq x$  values will be set to 0, whereas  $> x$  and  $\geq x$  values will be set to x.

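### Does putting fasted Day 7 and possibly non-fasted Day 14 chemistry in one safety-table row call for a change?

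*Protocol*

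**What the plan says.** **Fasting rule.** Check-in on Day -1 lists the "clinical chemistry panel [fasted at least 8 hours], coagulation parameters, hematology panel, and UA; Appendix 2" (Protocol 4.2). Appendix 4, footnote n, applies the same 8-hour fast to the in-house chemistry draws, including Day 7, and then lifts it: "At ET or the day before EOT (Day 14), subjects are not required to be fasted prior to clinical laboratory evaluations". Protocol 7.2.2 repeats the exception for early termination and the day before end of treatment: "subjects are not required to be fasted prior to clinical laboratory evaluations". The two places agree.

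**Labelling of days.** SAP 8.1.4 sends laboratory data to Table 4. There, study Day 7 is Day 7 of Period 1 with Day -1 as baseline. Study Day 14 is Day 7 of Period 2 with study Day 7 as baseline. The table's footnote adds: "Day 7 measurements will be summarized at day 7 for period 1 used as baselines for the period 2".

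**Summary.** SAP 8.6.2 says: "The observed results and change from baseline for clinical chemistry, hematology, and coagulation parameters will be summarized descriptively by treatment and period specific timepoint". It names no further split by period, sequence or study day. Layouts are left to the shells: "A detailed description of the planned TFLs to be presented in the clinical study report (CSR) is provided in the accompanying TFL shells document" (SAP 1).

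**Early-termination draws.** These do not reach the summary tables: "As ET data is not associated with any scheduled timepoint, it will be excluded from all calculations of summary statistics" (SAP 8.1.1).

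**The concern.** Subjects in sequence AB take the fed treatment in Period 2, and subjects in BA take the fasted treatment in Period 2. Read literally, each treatment's Day 7 chemistry row therefore takes half its values from study Day 7, where a fast was required, and half from study Day 14, where it was not. The mean change from baseline mixes in the same way. In Period 1 it is a fasted value minus a fasted value; in Period 2 it may be a non-fasted value minus a fasted one.

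For an analyte that responds to meals, the average in each column could carry a shift that a reader takes for a drug effect or a time effect. The chemistry table supports the secondary objective of safety and tolerability, so the natural suggestion is to show the two study days on separate rows, or to align the fasting rule by amendment.

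**Working it through.** The plan states no figure on this point, so there is none to reproduce. The check counts what falls in each row and works out how far a meal effect could move it.

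**Inputs**
- 10 subjects per sequence, 20 in all (Protocol 8.1); sequences AB and BA (Protocol 5.3).
- D: non-fasted minus fasted difference for an analyte. Not in the documents; left as a symbol.
- f: share of Day 14 draws actually non-fasted. Not in the documents; range 0 to 1.
- The chemistry analyte list in Appendix 2 was not legible in the text reviewed, so no analyte is named.

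**Step 1. Pooled row, complete data.** The fed column holds 10 AB values from Day 14 and 10 BA values from Day 7. The fasted column is the mirror image. The Day 14 share is 10/20 = 0.5 in each, so the shift in the mean, and in the mean change, is 0.5 f D:

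| f | shift in each column |
|---|---|
| 0 | 0 |
| 0.1 | 0.05 D |
| 0.25 | 0.125 D |
| 0.5 | 0.25 D |
| 1 | 0.5 D |

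The low end is plausible. Dosing is in the morning (Protocol 5.2) and 144 h = 6 × 24 h, so the draw is nominally a morning draw. Protocol 6.2 adds that "subjects will receive a standard diet at scheduled times that do not conflict with other study-related activities".

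**Step 2. Fed minus fasted.** With balanced sequences this moves by 0.5 f D − 0.5 f D = 0. If f differed by sequence, it would move by 0.5 D (f_AB − f_BA). An open-label study with one shared schedule gives no clear reason to expect that.

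**Step 3. Unequal sequences.** Suppose AB subjects are lost.
- One lost after Period 1: 9/19 − 10/20 = 0.474 − 0.500 = −0.026 f D.
- Two lost after Period 1: 8/18 − 10/20 = 0.444 − 0.500 = −0.056 f D.
- Two with neither draw: 8/18 − 10/18 = −0.111 f D.

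**Step 4. What a split by study day would do.**
- The Day 7 row would carry no meal shift. The Day 14 row would carry f D, twice the pooled 0.5 f D. Its change from baseline would still be a possibly non-fasted value minus a fasted one.
- Each mean would rest on 10 values instead of 20, so its standard error is √(20/10) = 1.41 times as large, at equal SD.
- On the Day 7 row, fasted would come from AB and fed from BA; on the Day 14 row, the reverse. Each row would compare different people. For observed values with common SD σ and within-subject correlation ρ, the variance of the fed-minus-fasted difference goes from 2σ²(1 − ρ)/20 in the pooled row to 2σ²/10 in a split row. The standard error ratio is √(2/(1 − ρ)), which is 1.41 at ρ = 0 and larger for any positive ρ. For change from baseline, each subject's own level is already subtracted, so less is lost there.
- If f differed by sequence, the Day 14 row would show D (f_AB − f_BA), twice the pooled figure. The split would not cure that either.

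**The case for a change.** The best case for acting is that nothing written in the SAP separates the two kinds of draw. Day 14 is a scheduled timepoint, so the early-termination exclusion does not remove it. A non-fasted Day 14 draw is permitted, so the review of deviations before database lock would not pick it up. Appendix 2 heads the chemistry panel as fasted, so a reader may assume every value was. Neither document names a data item for fasting state on Day 14. A split costs little programming, and cells of about 10 are well above the SAP's minimum of 3.

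These observations are correct, and what stands is that a reader of the pooled row could misread its absolute level. They do not support a split. The waiver is deliberate and stated the same way in both places, so there is nothing for an amendment to reconcile. Pooling the periods under one period-specific day is the SAP's general scheme; Table 3 does the same for ECGs and vital signs. Whether the chemistry table pools at all is settled in the shells, which were not available. The Table 4 footnote can also be read as display by period.

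A line under the table giving each day's fasting rule would tell the reader as much as a split, at no cost to the comparison. That is ordinary table annotation, and it alters no result.

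**Conclusion.** The reading of the documents is right, but no change to the plan follows. Under the pooled reading, the possible distortion is 0.5 f D in each treatment's Day 7 mean and mean change. It affects chemistry only, and f and D are not given in the documents. The fed-versus-fasted comparison, which is what the secondary objective concerns, moves by 0 with balanced sequences and equal f. It moves by at most about 0.11 f D in the two-subject loss cases worked above.

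Safety analysis is descriptive only (SAP 8.6.6). Every laboratory value is listed, with out-of-range results flagged and their clinical significance marked (SAP 8.6.2). The 72-hour draws are fasted in both periods under footnote n, and the primary PK analysis does not use these data. Splitting the row would exchange a small shift common to both columns for a larger one in the Day 14 row and a between-subject comparison. The pooled row is a fair trade-off. An explanatory table note is sensible reporting practice and can be left to those preparing the tables.
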